10.9. Analysis of safety

The primary analysis will be based on the TVC.

The percentage of subjects with at least one local AE (solicited and unsolicited), with at least one general AE (solicited and unsolicited) and with any AE during the solicited follow-up period will be tabulated with exact 95% CI after each vaccine dose and overall. The percentage of doses followed by at least one local AE (solicited and unsolicited), by at least one general AE (solicited and unsolicited) and by any AE will be tabulated for the overall vaccination course, with exact 95% CI. Similar tables will be generated for Grade 3 AEs and AEs considered as causally related to vaccination.

The percentage of subjects reporting each individual solicited local and general AE during the solicited follow-up period will be tabulated with exact 95% CI. The percentage of doses followed by each individual solicited local and general AE will be tabulated for each dose and for the overall vaccination course, with exact 95% CI. Similar tables will be generated for Grade 3 AEs, causal events and for fever, temperature in 0.5°C increments.

The proportion of subjects reporting an AE (unsolicited) until 30 days (Days 0-29) post each dose of RTS,S/AS01_E, classified by the Medical Dictionary for Regulatory Activities (MedDRA) preferred term level will be tabulated with exact 95% CI. The proportion of subjects reporting an AE (unsolicited) until 42 days (Days 0-41) after the administration of the YF vaccine and the combined measles and rubella vaccine

(restricted to the Coad group and Control group), classified by the MedDRA preferred term level will be tabulated with exact 95% CI.

The proportion of subjects reporting an SAE (all, fatal, related) occurring within 30 days (day of vaccination and 29 subsequent days) after each dose of study vaccines, classified by the MedDRA preferred term level will be tabulated with exact 95% CI.

The proportion of subjects reporting an SAE (all, fatal, related) from Day 0 to Month 4.5 and over the whole study duration (Day 0 to Month 33 for Coad and RTS,S groups and Month 36 for the Control group), classified by the MedDRA preferred term level will be tabulated with exact 95% CI.

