10.11. Conduct of analyses

Any deviation(s) or change(s) from the original statistical plan outlined in this protocol will be described and justified in the final study report.

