6.5. Analysis of safety

6.5.1. Analysis of safety planned in the protocol

The primary analysis will be based on the ES.

The percentage of subjects with at least one local AE (solicited and unsolicited), with at least one general AE (solicited and unsolicited) and with any AE during the solicited follow-up period [7 days post Dose 1, post Dose 2 and 14 days post Dose 3] will be tabulated with exact 95% CI after each vaccine dose and overall. The percentage of doses followed by at least one local AE (solicited and unsolicited), by at least one general AE (solicited and unsolicited) and by any AE will be tabulated for the overall vaccination course, with exact 95% CI. Similar tables will be generated for Grade 3 AEs and AEs considered as causally related to vaccination.

The percentage of subjects reporting each individual solicited local and general AE during the solicited follow-up period will be tabulated with exact 95% CI. The percentage of doses followed by each individual solicited local and general AE will be tabulated for each dose and for the overall vaccination course, with exact 95% CI. Similar tables will be generated for Grade 3 AEs, causal events and for fever, temperature in 0.5°C increments.

The proportion of subjects reporting an AE (unsolicited) until 30 days (Days 0-29) post each dose of RTS,S/AS01_E, classified by the Medical Dictionary for Regulatory Activities (MedDRA) preferred term level will be tabulated with exact 95% CI. The proportion of subjects reporting an AE (unsolicited) until 42 days (Days 0-41) after the administration of the YF vaccine and the combined measles and rubella vaccine (restricted to the Coad group and Control group), classified by the MedDRA preferred term level will be tabulated with exact 95% CI. Similar tables will be generated for Grade 3 AEs and AEs considered as causally related to vaccination.

The proportion of subjects reporting an SAE (all, fatal, related) occurring within 30 days (day of vaccination and 29 subsequent days) after each visit where a study product is potentially administered, classified by the MedDRA preferred term level will be tabulated with exact 95% CI.

The proportion of subjects reporting an SAE (all, fatal, related) from Day 0 to Month 4.5 and over the whole study duration (Day 0 to Month 33 for Coad and RTS,S groups and Month 36 for the Control group), classified by the MedDRA preferred term level will be tabulated with exact 95% CI.

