7. ANALYSIS INTERPRETATION

Except for analyses on objectives with a pre-defined success criterion (see Section 3), comparative analyses will be descriptive with the aim to characterize the difference in immunogenicity and safety between groups.

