11. ANNEX 1 STANDARD DATA DERIVATION RULE AND STATISTICAL METHODS

11.1. Statistical Method References

The exact two-sided 95% CIs for a proportion within a group will be the Clopper-Pearson exact CI [Clopper CJ, Pearson ES. The use of confidence or fiducial limits illustrated in the case of binomial. *Biometrika*. 1934;26:404-413].

The standardised asymptotic two-sided 95% CI for the group difference in proportions is based on the method described in the following paper: Robert G. Newcombe, interval estimation for the difference between independent proportions: comparison of eleven methods, *Statist Med*. 1998; 17, 873-890]. The standardised asymptotic method used is the method six.

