With dose received										
With Vitamin A received										
With RTS,S AS01E dose received										
With Measles and Rubella vaccine dose received										
With Yellow fever dose received										
With local solicited data available										
With RTS,S AS01E local solicited data available										
With Measles and Rubella local solicited data available										
With Yellow fever local solicited data available										
With general solicited data available										

Coad =

RTS,S =

Control =

n = for each dose: number of subjects enrolled in the considered cohort and fulfilling specific criteria for the considered dose

for all doses : sum of n from individual doses

per subject : number of subjects enrolled in the considered cohort and fulfilling specific criteria for at least one dose

% = percentage of doses with solicited/unsolicited data available among the number of administered doses

Template 26 Incidence and nature of solicited and unsolicited symptoms over 7 days post vaccination (Days 1-7) by dose and overall, per study group (Exposed Set)

		Any symptom				General symptoms				Local symptoms						
		95% CI				95% CI				95% CI						
	Group	N	n	%	LL	UL	N	n	%	LL	UL	N	n	%	LL	UL
Dose 1	Coad															
	RTS,S															
	Control											NA	NA	NA	NA	NA
Dose 2	Coad															
	RTS,S															
	Control											NA	NA	NA	NA	NA
Dose 3 (over 14 days)	Coad															
	RTS,S															
	Control															
Dose 3 (over 7 days)	Coad															
	RTS,S															
	Control															
Overall/dose	Coad															
	RTS,S															
	Control															
Overall/subject	Coad															
	RTS,S															
	Control															

Coad =

RTS,S =

Control =

For each dose and overall/subject:

N= number of subjects with at least one administered dose

n/%= number/percentage of subjects presenting at least one type of symptom whatever the study vaccine administered

For overall/dose:

N= number of administered doses

n/%= number/percentage of doses followed by at least one type of symptom whatever the study vaccine administered

95% CI = exact 95% confidence interval, LL = Lower Limit, UL = Upper Limit

Over 14 days post vaccination at Dose 3

Template 27 Incidence and nature of local solicited and unsolicited symptoms reported for each vaccine over 7 days post vaccination (Days 1-7) by dose and overall, per study group (Exposed Set)

			RTS,SAS01E					Measles and Rubella					Yellow fever				

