Overall/dose																
Drowsiness	All															
	Related															
	Grade 3															
	Grade 3*Related															
Irritability / fussiness	All															
	Related															
	Grade 3															
	Grade 3*Related															
Loss of appetite	All															
	Related															
	Grade 3															
	Grade 3*Related															
Temperature/ (Axillary) (°C)	All															
	Related															
	>39.0															
	>39.0*Related															
Measles/rube lla-like rash	All															
	Related															
	>39.0															
	>39.0*Related															

CONFIDENTIAL

200596 (MALARIA-073)
Statistical Analysis Plan Final

		Coad			RTS,S			Control								
		95 % CI			95 % CI			95 % CI								
Symptom	Type	N	n	%	LL	UL	N	n	%	LL	UL	N	n	%	LL	UL
Overall/subject																
Drowsiness	All															
	Related															
	Grade 3															
	Grade 3*Related															
Irritability / fussiness	All															
	Related															
	Grade 3															
	Grade 3*Related															
Loss of appetite	All															
	Related															
	Grade 3															
	Grade 3*Related															
Temperature/ (Axillary) (°C)	All															
	Related															
	>39.0															
	>39.0*Related															
Measles/rube-lla-like rash	All															
	Related															
	>39.0															
	>39.0*Related															

Coad =

RTS,S =

Control =

For each dose and overall/subject:

N= number of subjects with at least one administered dose

n/%= number/percentage of subjects reporting the symptom at least once

For Overall/dose:

N= number of administered doses

n/%= number/percentage of doses followed by at least one type of symptom

95%CI= Exact 95% confidence interval; LL = lower limit, UL = upper limit

Solicited symptoms are reported over 14 days post Dose 3

Template 35 Maximum temperature reported during the 7-day (Days 1-7) post-vaccination period (overall doses), per study group (Exposed Set)

Characteristics	Categories	Coad N =				RTS,S N =				Control N =			
		n	%	LL	UL	n	%	LL	UL	n	%	LL	UL
Maximum temperature	No fever												
	Unknown temperature												
	[37.5-38.0]												
	[38.1-38.5]												
	[38.6-39.0]												
	[39.1-39.5]												
	[39.6-40.0]												
	>40.0												

Coad =

RTS,S =

Control =

N = number of doses

n = number of doses in a given category

% = n / Number of doses with available results x 100

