Level 1: Witnessed sudden loss of consciousness AND generalized, tonic, clonic, tonic-clonic, or atonic motor manifestations

Level 2: History of unconsciousness AND generalized, tonic, clonic, tonic-clonic, or atonic motor manifestations

Level 3: History of unconsciousness AND other generalized motor manifestations

Level 4: Reported generalized convulsive seizure with insufficient evidence to meet the case definition

Level 5: Not a case of generalized convulsive seizure

Within 14 days post Dose 3

Template 45 Incidence of concomitant medication administered during the <30-day (Days 1-30)> post-vaccination period by dose and overall, per study group (Exposed Set)

	Coad			RTS,S			Control								
				95% CI					95% CI					95% CI	
	N	n	%	LL	UL	N	n	%	LL	UL	N	n	%	LL	UL
Dose 1															
Any antipyretic															
Prophylactic antipyretic															
Dose 2															
Any antipyretic															
Prophylactic antipyretic															
Dose 3															
Any antipyretic															
Prophylactic antipyretic															
Overall/dose															
Any antipyretic															
Prophylactic antipyretic															
Overall/subject															
Any antipyretic															
Prophylactic antipyretic															

Coad =

RTS,S =

Control =

For each dose and overall/subject:

N= number of subjects with at least one administered dose

n/%= number/percentage of subjects who started to take the specified concomitant medication at least once during the mentioned period

For overall/dose:

N= number of administered doses

During the < 42-day> post-vaccination period post Dose 3

Template 46 Number (%) of subjects with serious adverse events including number of events reported during the study period (Exposed Set)

					Coad N =			RTS,S N =			Control N =		
Type of Event	Primary System Organ Class	Preferred Term (CODE)	n*	n	%	n*	n	%	n*	n	%		
SAE	At least one symptom												
	<each SOC>	<each PT term>											
Related SAE	At least one symptom												
	<each SOC>	<each PT term>											
Fatal SAE	At least one symptom												
	<each SOC>	<each PT term>											
Related fatal SAE	At least one symptom												
	<each SOC>	<each PT term>											

Coad =

RTS,S =

Control =

N = number of subjects with the administered dose

n* = number of events reported

n/% = number/percentage of subjects reporting the symptom at least once

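### Exact confidence intervals on pooled dose counts treat up to three doses per child as independent in the Coad and RTS,S columns, so they are too narrow for common reactions if reactions correlate within a child

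*SAP*

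**What the plan says.** SAP section 6.5.1, following protocol section 10.9, plans two kinds of pooled-dose summary. The first is the percentage of doses followed by a local AE, by a general AE "and by any AE will be tabulated for the overall vaccination course, with exact 95% CI". The second covers each individual solicited event, whose percentage of doses "will be tabulated for each dose and for the overall vaccination course, with exact 95% CI" (protocol section 10.9; same rule in the SAP).

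SAP section 11.1 fixes the method: "The exact two-sided 95% CIs for a proportion within a group will be the Clopper-Pearson exact CI".

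SAP Annex 3 shows where the rule lands:
- **Templates 26 to 34** have Overall/dose rows whose N is the number of administered doses. The Template 26 footnote defines the count as "n/%= number/percentage of doses followed by at least one type of symptom whatever the study vaccine administered".
- **Template 35** (maximum temperature, all doses) computes its percentage as "n / Number of doses with available results x 100", with exact limits.
- **Template 45** ("Incidence of concomitant medication administered during the <30-day (Days 1-30)> post-vaccination period by dose and overall") has an Overall/dose row for antipyretics with a 95% interval.

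The solicited follow-up in section 6.5.1 covers three doses. Neither document mentions repeated doses in the same child, a cluster-robust variance or a caveat. The same tables also carry single-dose and Overall/subject rows.

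**The concern.** Clopper-Pearson limits are exact for independent yes/no outcomes with a common probability. Three doses in one child are repeated measurements. A child who reacts to one dose may be more likely to react to the next. With positive correlation, 699 doses from 233 children carry less information than 699 doses from 699 children, and an interval built on 699 is too short.

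At stake is how these summary rows are read. For common reactions such as pain or fever they would show more precision than the data support, under a 95% label. The percentages themselves are not biased.

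**Working it through.** **Inputs from the documents**
- Group size: protocol section 10.4 plans 205 evaluable children per group with about 12% loss. 205 / 0.88 = 233, as stated.
- Doses per child in Coad and RTS,S: three (Visits 2, 3 and 4; protocol section 6.3). Doses per group: 233 x 3 = 699. This equals the trial's planned total of 699 children only by coincidence.
- Interval: two-sided 95% Clopper-Pearson.

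**Assumed inputs** (not in the documents)
- Within-child correlation on the yes/no scale, rho: 0, 0.1, 0.3, 0.5.
- Per-dose event rate: 0.5, 5, 10 and 30%.

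**Design effect.** With m doses per child and equal rates, the variance of the pooled percentage is p(1 - p)/699 multiplied by 1 + (m - 1) x rho. With m = 3 this is 1 + 2 x rho.

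For 210 of 699 doses (30%), the interval as planned is 26.7 to 33.6%, a width of 6.9 points. Clopper-Pearson on effective doses gives:

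| rho | Design effect | Effective doses | Interval | Width against planned |
|---|---|---|---|---|
| 0.1 | 1.2 | 699/1.2 = 582.5 | 26.3-33.9% | 10% wider |
| 0.3 | 1.6 | 699/1.6 = 436.9 | 25.8-34.6% | 27% wider |
| 0.5 | 2.0 | 699/2.0 = 349.5 | 25.3-35.1% | 42% wider |

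A normal-theory clustered interval gives 7, 24 and 39% wider.

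**Coverage of the planned 95% interval** (beta-binomial simulation, 233 children x 3 doses, 40,000 runs per cell):

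| Rate | rho 0 | 0.1 | 0.3 | 0.5 |
|---|---|---|---|---|
| 30% | 95.8 | 93.7 | 89.1 | 84.4 |
| 10% | 95.5 | 93.7 | 89.3 | 84.6 |
| 5% | 96.2 | 94.4 | 89.8 | 85.7 |
| 0.5% | 99.1 | 98.2 | 96.8 | 95.4 |

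At 0.5% the exact method's own conservatism absorbs the clustering, so rare events are not under-covered.

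**Unequal dose rates.** If rates differ by dose number, the binomial variance is slightly too large even under independence. For 10/30/50% the ratio of true to binomial variance is (0.09 + 0.21 + 0.25)/(3 x 0.21) = 0.55/0.63 = 0.87. For 20/30/40% it is 0.61/0.63 = 0.97. With rates 50/30/10% and a latent-normal model, coverage is 96.3, 95.4 and 94.4% at latent correlations of 0.1, 0.174 and 0.3. With 40/30/20%, coverage is 94.1, 89.2 and 85.1% at yes/no correlations of 0.1, 0.3 and 0.5. Strong differences between doses can therefore cancel a small correlation; modest differences do not cancel a moderate one.

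**Control column.** SAP section 11.2.5 counts, per dose, study visits at which a study vaccine was given. Among Visits 2 to 4 a Control child has one, Visit 4; Visit 2 is Vitamin A only and nothing is given at Visit 3. That is one outcome per child, so the exact interval is valid there.

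**The case against.** The strongest reply is that nothing turns on these rows. SAP section 7 says that, outside the objectives with a success criterion, "comparative analyses will be descriptive with the aim to characterize the difference in immunogenicity and safety between groups". Point estimates are unchanged. The Coad against RTS,S comparison at Dose 3, where the two groups' injections differ, has its own row with a valid interval, and so does the per-child summary. All of this stands and keeps the point small. It does not make a 95% label correct on an interval that may cover 90% of the time.

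The second reply is that the size is wholly assumed. That also stands. At a correlation of 0.1 the loss is only one to two points of coverage. Unequal dose rates, plausible because Dose 3 has a longer solicited window and in Coad more injections, can remove it.

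A third reply is that a footnote would do. A footnote warns the reader but leaves the mislabelled interval in place; omitting the interval is just as cheap.

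Four stronger readings are tempting but not supported:
- **All three columns are affected.** Templates 26 and 34 do show Control general-symptom rows for Doses 1 and 2, but the per-dose denominator in SAP section 11.2.5 leaves one outcome per Control child.
- **Control Visits 2 and 3 should be counted as doses so that columns match.** That would change the quantity estimated. With assumed rates of 30% after Visit 4 and 5% after each earlier visit, 30% becomes (30 + 5 + 5)/3 = 13.3%. It would also create clustering where there is none.
- **Seizure rates per 1000 doses (Template 42) are under-covered.** The 0.5% row of the coverage table shows no under-coverage for rare events.
- **The safety conclusions are unsound.** The valid rows beside the pooled ones and the descriptive purpose rule this out.

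**Conclusion.** The point holds for the pooled-dose rows of Templates 26 to 34 and 45, and for Template 35, in the Coad and RTS,S columns and for common reactions. It is conditional on positive within-child correlation. With 233 children, three doses each and equal rates of 5 to 30%, coverage is about 93-94% at a correlation of 0.1, 89-90% at 0.3 and 84-86% at 0.5. The last is the far end of an assumed range, not an expected value. Under-coverage is smaller, or absent, when dose rates differ strongly and correlation is small.

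Single-dose rows, Overall/subject rows, the one-dose measles-rubella and yellow fever columns, rare events and the Control column are unaffected. No success criterion or formal decision changes. It is worth correcting because it is cheap, but it is a matter of presentation.

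**What to change.** Choose one of two rules for the pooled-dose rows named above.

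1. **Child-clustered interval.** Use Clopper-Pearson on doses divided by the child-level design effect, estimated from the data and floored at 1. In simulation over the same correlations this covers between about 95 and 97% at rates of 5, 10 and 30%. Print no pooled interval in sparse or zero cells (many Grade 3 rows), with the cut-off stated in advance. The design effect cannot be estimated without events, and 0/699 doses would print an upper limit of 0.53% where 0/233 children gives 1.57%.
2. **No interval.** Print the pooled-dose percentage alone and rely on the exact Overall/subject interval.

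Either rule departs from protocol section 10.9. Record it in SAP section 9, which now lists only the anti-CS threshold change, and justify it in the report, since protocol section 10.11 says "Any deviation(s) or change(s) from the original statistical plan outlined in this protocol will be described and justified in the final study report". Leave the Control dose numbering and denominators as they are.

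The cost is a little programming and one SAP entry, with no new data. Under rule 1 the intervals at a 30% rate widen by about 10, 27 or 42% at correlations of 0.1, 0.3 or 0.5, and hardly at all if there is no correlation. Under rule 2 these rows lose their intervals.

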1.2.3. Rationale for safety follow-up

Safety and reactogenicity for the RTS,S/AS01_E have previously been evaluated, alone or in co-administration with EPI vaccines given between 6-12 weeks of age. However, safety has not been evaluated in co-administration with measles, rubella and YF in a 0, 1.5, 3-month schedule starting at 6 months of age. This study will therefore provide safety information when RTS,S/AS01_E is administered at 6, 7.5 and 9 months of age alone or in co-administration with YF vaccine and a combined measles and rubella vaccine.

A 12-month safety follow-up after the last dose of RTS,S/AS01_E vaccine will be applied to all study groups.

Contrary to the 7-day follow-up period after RTS,S/AS01_E vaccination in other malaria clinical studies, a 14-day follow-up safety period will be applied in this study following the study vaccines administered at 9 months of age (Visit 4) because, in combined measles and rubella vaccines, the peak of fever usually occurs between 5-12 days post-vaccination [Shinefield, 2005].

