^a Study personnel will visit the children on Days 1, 2, 3, 4, 5 and 6 after Vitamin A administration (Visit 2) and after Visit 3 to record solicited general and unsolicited AEs on diary cards.^b Study personnel will visit the children on Days 1, 2, 3, 4, 5, 6, 7, 8, 9, 10, 11, 12, and 13 after vaccination to record solicited and unsolicited AEs on diary cards.^c Collection of solicited local AE for the two injection sites.^d Seizures occurring within 30 days post-vaccination for vaccine doses administered at 6 and 7.5 months of age (Visits 2 and 3) or 42 days post-vaccination for vaccine doses administered at 9 months of age (Visit 4).

Note: The double-line border following Month 4.5 (Visit 6) indicates the analyses which will be performed on all data (i.e. data that are as clean as possible) obtained up to Month 4.5.

* If the investigator believes there is a reasonable reason to do so, screening procedures may only be repeated once.

† Confirmatory serology tests should be performed to identify cases of vaccine failure.

● is used to indicate a study procedure that requires documentation in the individual eCRF.

○ is used to indicate a study procedure that does not require documentation in the individual eCRF.

Table 7 Intervals between study visits (Amended: 09 August 2016)

Study visit	Timing of visit ^a	Allowed interval ^b
Visit 1 (Screening) ^c	1-28 days before Visit 2	-
Visit 2	6 months of age	Child should be 6 ^c months of age
Visit 3	7.5 months of age	Child should be 7 ^d or 8 ^e months of age but respecting a minimum of 4 weeks (28 days) since previous dose (Visit 2)
Visit 4	9 months of age	Child should be 9 ^f months of age but respecting a minimum of 4 weeks (28 days) since previous dose (Visit 3)
Visit 5	4 weeks after Visit 4	Minimum 4 weeks (28 days) - Maximum 6 weeks (42 days)
Visit 6	2 weeks after Visit 5	Minimum 2 weeks (14 days) - Maximum 3 weeks (21 days)
Visit 7	4 weeks after Visit 6	Minimum 4 weeks (28 days) - Maximum 6 weeks (42 days)
Visit 8	4 weeks after Visit 7	Minimum 4 weeks (28 days) - Maximum 6 weeks (42 days)
Visit 9	4 weeks after Visit 8	Minimum 4 weeks (28 days) - Maximum 6 weeks (42 days)
Visit 10	18 months after Visit 4	17 months (516 days) after Visit 4 – 19 months (577 days) after Visit 4
Visit 11	4 weeks after Visit 10	Minimum 4 weeks (28 days) - Maximum 6 weeks (42 days)
Visit 12	17.5 months after Visit 8	17 months (516 days) after Visit 8 – 19 months (577 days) after Visit 8

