Visit 13	4 weeks after Visit 12	Minimum 4 weeks (28 days) - Maximum 6 weeks (42 days)
Visit 14	12 months after Visit 10	11 months (334 days) after Visit 10 - 13 months (396 days) after Visit 10
Visit 15	12 months after Visit 12	11 months (334 days) after Visit 12 - 13 months (396 days) after Visit 12

^a Whenever possible the investigator should arrange study visits within this interval.

^b Subjects will not be eligible for inclusion in the ATP cohort for analysis of immunogenicity if they make the study visit outside this interval.

^c For clarity this corresponds from the day the child becomes 6 months of age until the day before the child achieves 7 months of age.

^d For clarity this corresponds from the day the child becomes 7 months of age until the day before the child achieves 8 months of age.

^e For clarity this corresponds from the day the child becomes 8 months of age until the day before the child achieves 9 months of age.

^f For clarity this corresponds from the day the child becomes 9 months of age until the day before the child achieves 10 months of age.

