2. STUDY DESIGN

Figure 1 Study design

- Experimental design: Phase IIIB, open, randomized, controlled, multi-centric study with three parallel groups.
- Duration of the study: Approximately 33 months per participant in the Coad or the RTS,S group and 36 months in the Control group.
 - Epoch 001: Primary starting at Visit 1 (Screening) and ending at Visit 15 (Month 36).
- Study groups: 3 study groups are defined for the study (Coad group, RTS,S group and Control group). A description of the vaccination, blood sample and visit schedule is provided for each of the study groups in [Figure 1](#).

Table 1 Study groups and epochs foreseen in the study

Study groups	Number of subjects	Age (Min)	Epoch 001
Coad group	233	6 months*	X
RTS,S group	233	6 months*	X
Control group	233	6 months*	X

* For clarity this corresponds from the day the child becomes 6 months of age until the day before the child achieves 7 months of age.

Table 2 Study groups and treatment foreseen in the study

Treatment name	Vaccine/Product name	Study groups		
		Coad group	RTS,S group	Control group
RTS,S/AS01 _E	RTS,S	X	X	X
	AS01E	X	X	X
Yellow fever	WHO prequalified Yellow Fever	X	X	X
Measles and Rubella	MR-VAC	X	X	X
Vitamin A	Vitamin A	X	X	X

MR-VAC: Live attenuated measles virus and rubella virus vaccine (Serum Institute of India)

- Treatment allocation: randomized in a 1:1:1 ratio to each study group.
- Blinding: open

Table 3 Blinding of study epoch

Study Epoch	Blinding
Epoch 001	open

- Type of study: self-contained.
- Data collection: Electronic Case Report Form (eCRF).
- Safety monitoring: description of safety monitoring is available in [Table 5](#)
- Immunogenicity monitoring:

Table 4 Immunological read-outs

Blood sampling timepoint		study group	No. subjects	Component	Components priority rank
Type of contact and timepoint	Sampling timepoint				
Visit 2	Day 0	Coad group and RTS,S group	466	anti-CS	1
		Coad group and RTS,S group	466	anti-HBs	2
		Coad group and Control group	466	anti-catalase	3
Visit 4	Month 3	Coad group and Control group	466	anti-Me	1
		Coad group and Control group	466	anti-Ru	2
Visit 5	Month 4	Coad group and RTS,S group	466	anti-CS	1
		Coad group and RTS,S group	466	anti-HBs	5
		Coad group and Control group	466	anti-catalase	6
		Coad group and Control group	466	anti-Me	2
		Coad group and Control group	466	anti-Ru	3
		Coad group and Control group	466	anti-YF	4

Table 5 Reporting periods for adverse events and serious adverse events

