The proportion of subjects reporting an AEs of specific interest (pIMDs, meningitis and seizures) from Day 0 to Month 4.5 and over the whole study duration (Day 0 to Month 33 for Coad and RTS,S groups and Month 36 for the Control group), classified by the MedDRA preferred term level will be tabulated with exact 95% CI.

For generalized convulsive seizures occurring within 7 days after vaccines administered at Visit 2 and 3 (Coad and RTS,S groups) and 14 days after vaccines administered at Visit 4 (all groups) an analysis will be performed based on the Brighton Collaborations guidelines [**Bonhoeffer**, 2004]. This includes descriptive tables of the time relationship of seizures to vaccination, the duration of seizures and the level of diagnostic certainty.

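### Whole-study SAE, pIMD and meningitis percentages cover 33 months in Coad and RTS,S but 36 in Control, with no allowance for time, so they are not directly comparable with Control

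*SAP*

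**What the plan says.** SAP 6.5.1, repeating Protocol 10.9, defines the long-term SAE summary as "The proportion of subjects reporting an SAE (all, fatal, related) from Day 0 to Month 4.5 and over the whole study duration", with exact 95% CIs by group. The next paragraph does the same for pIMDs, meningitis and seizures "over the whole study duration (Day 0 to Month 33 for Coad and RTS,S groups and Month 36 for the Control group". SAP section 2 gives the planned duration as "Approximately 33 months per participant in the Coad or the RTS,S group and 36 months in the Control group".

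SAP 11.2.5 sets the counting rule. The analysis includes every child given a study vaccine or Vitamin A, and a child with no report of an event is treated as not having had it. Template 46, the mock table for SAEs over the study period, shows number of events, number of children and percentage for the three groups. Neither document plans a rate per unit of time, a time-to-event estimate or a common cut-off later than Month 4.5.

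The difference in length is deliberate. Protocol 1.2.3 states: "A 12-month safety follow-up after the last dose of RTS,S/AS01_E vaccine will be applied to all study groups". Control has its last dose later, so it ends later.

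**The concern.** A cumulative percentage can only rise as observation lengthens. When three percentages sit side by side and one covers three more months, the longer one tends to be higher even if the underlying risk is identical. Here the longer one is always Control. Early withdrawals add to the problem: a child who leaves early without an event counts as fully observed, and this could distort any pair of groups if withdrawal differs.

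SAP section 7 says that the descriptive comparisons are meant to characterise the safety difference between groups. Between Month 4.5 and study end, apart from the 30-day post-dose windows, these percentages are the only group summary specified for SAEs, deaths, pIMDs and meningitis. Protocol 1.3.1 lists meningitis and pIMD as important potential risks of RTS,S/AS01E, so readers will look at this table.

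**Working it through.** **1. Reproduce the stated durations** (Protocol Table 7 for intervals; Tables 4 to 6 for nominal months).

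- Coad and RTS,S: Visit 4 at Month 3; booster "18 months after Visit 4"; final visit "12 months after Visit 10". 3 + 18 + 12 = 33.
- Control: Visit 8 at Month 6.5; booster "17.5 months after Visit 8"; final visit "12 months after Visit 12". 6.5 + 17.5 + 12 = 36.

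Both agree with the SAP. The ratio is 36/33 = 1.091, or 9.1% more follow-up in Control.

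**2. Effect on a cumulative percentage at equal risk.** Let P33 be the 33-month risk. At constant hazard, P36 = 1 − (1 − P33)^(36/33). If hazard in the last three months is a fraction f of the earlier average, the exponent becomes 1 + 3f/33. The documents give no event risks, so every P33 below is an assumption.

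| Assumed P33 | P36, constant hazard | Excess, points | Children of 233 | P36, f = 0.5 |
|---|---|---|---|---|
| 1% | 1.09% | 0.09 | 0.2 | 1.05% |
| 5% | 5.44% | 0.44 | 1.0 | 5.22% |
| 10% | 10.86% | 0.86 | 2.0 | 10.43% |
| 20% | 21.61% | 1.61 | 3.7 | 20.81% |
| 30% | 32.23% | 2.23 | 5.2 | 31.13% |
| 50% | 53.05% | 3.05 | 7.1 | 51.55% |

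**3. Upper limit at constant hazard.** The relative excess approaches 36/33 − 1 = 9.1% as risk becomes small. For the absolute excess, put s = 1 − P33; the gap is s − s^(12/11), largest at s = (11/12)^11 = 0.384. That is P33 = 61.6%, where the gap is 0.384/12 = 3.2 points.

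**4. Against sampling error.** With 233 children and a risk of about 20%, the exact 95% CI is 15.2% to 25.9%. The 1.6-point excess is well inside it.

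**5. Would a rate remove it?** A risk of 20% over 33 months is −ln(0.80) × 12/33 = 0.081 per child-year. A risk of 21.61% over 36 months is −ln(0.7839) × 12/36 = 0.081. The rates agree where the percentages do not.

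**6. Seizures.** The endpoint in SAP 4.2 counts seizures only within 30 or 42 days of specified doses. Control's last window opens at the Month 24 booster and closes at about Month 25, so Months 33 to 36 cannot add a case.

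**7. Cutting all groups at Month 33 instead.** Time after booster would be 33 − 24 = 9 months in Control against 33 − 21 = 12 in the others, which undoes the equality that Protocol 1.2.3 intends.

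**The case against.** The case for leaving the plan alone is substantial.

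- **The stated contrast is unaffected.** The safety objective (SAP 3.2) compares co-administration with RTS,S/AS01E given alone. Both groups have 33 months. This stands; a rate would help that contrast only if withdrawal differs.
- **Control is not free of RTS,S/AS01E.** A reader might infer that the bias makes the malaria vaccine look safer than no malaria vaccine. The documents do not support that. Control receives three doses from Month 4.5 and a booster at Month 24, so each group is scheduled for four. Over the whole study the Control contrast is earlier against later vaccination. The period before Control's RTS,S/AS01E course is covered by the Month 4.5 tables, which use the same window in all groups.
- **The effect is small, and safety is descriptive.** No safety test or success criterion exists, both durations are stated, and for rare events such as meningitis the excess may be a fraction of a child. This stands as an argument about priority. It does not make the percentages comparable: a systematic offset is not cured by the absence of a test.
- **The unequal length is intended.** It gives every group 12 months after its last dose. That justifies the design, but not an unadjusted percentage, and a rate keeps the full 12 months.
- **Collection might start later in Control.** Protocol 8.2.1 begins SAE and AE-of-specific-interest collection at the first study vaccine. Read literally, that is Month 3 in Control if Vitamin A is not counted, giving 36 − 3 = 33 months. Against this, the Control schedule (Protocol Table 6) records these events from Visit 2, SAP 4.2 starts SAEs at screening and the specific-interest events at Day 0, and SAP 6.5.1 analyses from Day 0. The Day 0 reading is the one used here, but these sections need reconciling.

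**Conclusion.** The point holds for SAEs (all, fatal, related), pIMDs and meningitis, and only for comparisons with Control. At equal risk, Control's whole-study percentage is biased upward by at most 9.1% relative and about 3.2 points. These limits assume constant hazard. The excess is roughly halved if late hazard is half the earlier average, and would exceed the limits only if hazard rose late in follow-up. Event risks are assumed throughout, and 33 and 36 months are nominal lengths.

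Three wider conclusions should not be drawn: that the co-administration safety comparison is biased by the 33/36 split, that seizure percentages are raised by the extra three months, or that the longer Control follow-up is itself an error. This is a minor point, worth acting on because the direction of the bias is known and the remedy is cheap.

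**What to change.** In the whole-study tables for SAEs (all, fatal, related), pIMDs and meningitis, add for each group the number of children with a first event per child-year, with an exact Poisson 95% CI. Time runs from Day 0 to first event, withdrawal or study end, whichever comes first. Keep the percentages, with a footnote that they cover 33 months in Coad and RTS,S and 36 in Control. State explicitly when observation starts in Control, so that Protocol 8.2.1 and SAP 6.5.1 agree. Record the addition in SAP section 9.

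The cost is one extra column, a footnote and some SAP wording; the dates needed are already collected. The downside is that a rate averages over a hazard that may change with age. A common Month 33 cut is the weaker option, because it leaves Control with 9 months after booster against 12.
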